### 5.6 Strategies for Recruitment

Investigators will identify potential subjects in the setting of their outpatient clinics. This study will be posted on clinicaltrials.gov for help in recruitment. Investigators will perform local and regional outreach to patients and physicians. Furthermore, we will enlist the help of patient education and advocacy forums such as national cooperative groups, Lymphoma Research Foundation, The CLL Society and Leukemia & Lymphoma Society for advertisement of the trial.

### 5.7 Number of Study Sit es

This is a two-institution study including The University of Utah/Huntsman Cancer Institute (Salt Lake City, UT) and MD Anderson Cancer Center (Houston, TX).

If trial recruitment is anticipated to be greater than the expected maximum of 36 months, then additional CLL specialty centers will be asked to participate in this trial.

# 6 STUDY INTERVENTION

### 6.1 Administration Schedule

Treatment will be administered on an outpatient basis. No investigational or commercial agents or therapies other than those described below may be administered with the intent to treat the patient's CLL.

Regimen Description					
Agent	Precautions	Dose	Route	Schedule	Cycle Length
RP-3500	Take with 8 oz of water at approximately the same times each day (±2 hours)	Capsule*	Oral	Once daily; intermittent weekly dosing of 2 days on and 5 days off	21 days (3
Olaparib	Take with 8 oz of water at approximately the same times each day (±2 hours)	Capsule*	Oral	Twice daily; intermittent weekly dosing of 2 days on 5 days off	weeks)
* Doses as appropriate for assigned dose level					

Study medications should be taken at approximately the same time every day. Study medication should not be crushed, chewed, or altered in any way. Subjects should not take extra medication for any reason nor should they re-administer in the case of vomiting after

administration. If a dose is missed outside of the dosing window, the dose should not be made up but rather dosing should continue at their regularly scheduled time.

# 6.1.1 Preparation and Dispensing

The investigator or qualified personnel will prepare and dispense all investigational supplies. Subjects will be dispensed enough medication to last a full cycle of both study medications. Appropriate records will be kept to accurately show all dispensing activates and Investigational Product (IP) will be supplied only to subjects deem eligible for study therapy. IP may not be dispensed to subjects who have not been enrolled in the trial.

## 6.1.2 Accountability and Compliance

Information pertaining to study drug compliance (i.e., date time, and dose) will be recorded by subjects on the drug diary (see Appendix 3) and recorded in the corresponding electronic case report form (eCRF) by the study team. A member of the study team will review subject drug compliance at the end of each cycle and provide subject re-education as required. Any reason for non-compliance will be documented in the subject's research chart and the corresponding eCRF. At the discretion of the principal investigator, a subject may be discontinued from the trial for non-compliance with study visits or study drug.

Subjects will be required to return any unused medication or empty bottles at the end of every cycle. Excess or unused study drug should be returned to the investigative site for accounting and destroyed in accordance with GCP after drug accountability has been performed. The total number of tablets dispensed, returned, and documented as taken will be reconciled to support drug accountability. Treatment compliance will be calculated and recorded separately for each drug. It will be recorded as a percentage defined as the number of doses taken divided by the expected number of doses taken multiplied by 100%.

## 6.2 Olaparib

## 6.2.1 Investigational Product Supplies

Olaparib will be supplied by Repare Therapeutics as either 150mg or 100mg tablets.

• 150 mg: green to green/grey, oval, bi-convex, film-coated, with debossment 'OP150' on one side and plain on the reverse side.

• 100 mg: yellow to dark yellow, oval, bi-convex, film-coated, with debossment 'OP100' on one side and plain on the reverse side.

Olaparib will be stored at 20°C to 25°C (68°F to 77°F), excursions permitted to 15°C to 30°C (59°F to 86°F). Tablets will be stored in original bottle to protect from moisture.

The Principal Investigator will ensure appropriately trained and delegated personnel will receive, inventory, and stored all investigational products per applicable laws and regulations.

## 6.3 Camonsertib (RP-3500)

## 6.3.1 Investigational Product Supplies

RP-3500 will be supplied by Repare Therapeutics as capsules containing 5 mg or 40 mg (free base equivalent) of RP-3500 hydrogen sulfate salt. Capsules are packaged in induction-sealed HDPE bottles fitted with child-resistant polypropylene caps. The study drug should be stored in the original bottles tightly closed in a dry place at 15 to 25°C (59 to 77°F). The capsules should not be frozen.

### 6.4 Dose Interruptions

Dose interruptions for study treatment-related AEs are allowed as per the dose modification recommendations in Section 6.6. In addition to dose interruption, the need for a dose reduction at the time of treatment resumption should also be considered based on the dose modification recommendations. If a toxicity-related dose delay lasts for >28 days, treatment will be discontinued permanently and the subject should be removed from study treatment. If a subject requires a dose hold for > 28 days for a non-treatment-related adverse event or situation (i.e. radiation therapy or COVID-19 infection) the subject may continue on study only after approval and discussion with the Principal Investigator and Medical Monitor.

All doses that were missed for any reason will not be replaced.

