#### General

- a. Treatment delays > 21 days.
- b. Any grade 5 event.

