## 6.6 Dose Modifications and Supportive Care Guidelines

Subjects experiencing AEs attributed to study drug may undergo dose modifications for toxicity management. Dose modification guidelines are provided below for AEs considered to be related to study medication.

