The order in which dose reductions will occur will be change in dosing schedule (Table 10.: Dosing Schedule Modifications) with either sequential (preferred) or concurrent changes in drug dosages (Table 11). If drug dosage changes are required, the order in which dose reductions will occur will be camonsertib (RP-3500) first followed by olaparib if the AE continues to occur. If at any time a dose reduction would leave camonsertib (RP-3500) or olaparib doses less than DL 1 (Table 11. Dose Reduction Levels), the patient will be taken off protocol. Treatment delays for adverse events exceeding 21 days will lead to protocol removal. If reduction of the dosing schedule and/or drug doses resolves the patient's toxicity to grade  $\leq 1$  for at least 3-6 weeks, increasing camonsertib (RP-3500) and/or olaparib back to the prior dose or dosing schedule is permitted after discussion with the study PI.

Event Name	Neutropenia	
Grade of Event	Management/Next Dose for RP - 3500	Management/Next Dose for Olaparib
≤ Grade 1	No change in dose	No change in dose
Grade 2	No change in dose	No change in dose
Grade 3	No change in dose	No change in dose
Grade 4	Hold until ANC ∫ is ≥1000/mm  . G- CSF administration is recommended. At first occurrence, no change in dose or dosing schedule. If toxicity recurs, follow reductions in dosing schedule and drug dosages as per sections 6.6.1 and 6.6.2 only if grade 4 neutropenia lasts ≥7 days with optimal supportive care.	Hold until ANC ∫ is ≥1000/mm  . G- CSF administration is recommended. At first occurrence, no change in dose or dosing schedule. If toxicity recurs, follow reductions in dosing schedule and drug dosages as per sections 6.6.1 and 6.6.2 only if grade 4 neutropenia lasts ≥7 days with optimal supportive care and

Table 13. Management and dose modification guidelines for hematologic toxicities encountered with combination camonsertib (RP-3500) and olaparib.

6.6.2 if RP-3500 dosage already

		RP-3500 dosage already decreased for the same toxicity.	
j Only for patients with ANC $\geq$ 500/mm 	 Only for patients with baseline ANC $\geq$ 1000. For patients with baseline ANC <1000, hold until ANC $\geq$ 500/mm 		
Event Name	Thromboc	ytopenia	
Grade of Event	Management/Next Dose for RP - 3500	Management/Next Dose for Olaparib	
≤ Grade 1	No change in dose	No change in dose	
Grade 2	No change in dose	No change in dose	

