upon investigator discussions. If treatment delay is >7 days but ≤21 days, restart treatments following reductions in dosing schedule and drug dosages as per sections 6.6.1 and 6.6.2 in which changes in dosing schedule of both drugs should first be implemented with either sequential or concurrent reductions in drug dosages. If treatment delay >21 days, discontinue study.

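### Section 6.4 stops treatment after a toxicity delay of more than 28 days, while 6.6.3, 6.6.5 and Table 14 stop it after more than 21 days, and nothing says which limit governs a delay of 22 to 28 days

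*Combined protocol and SAP*

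**What the plan says.** Section 6.4 sets a limit for delays caused by toxicity: "If a toxicity-related dose delay lasts for >28 days, treatment will be discontinued permanently and the subject should be removed from study treatment". The same section sends the reader elsewhere for how to interrupt: "Dose interruptions for study treatment-related AEs are allowed as per the dose modification recommendations in Section 6.6". Section 6.6 states its own scope as drug-related events: "Dose modification guidelines are provided below for AEs considered to be related to study medication".

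Within Section 6.6 the limit is shorter. Section 6.6.3 (hematologic and infectious toxicity) says: "Treatment delays for adverse events exceeding 21 days will lead to protocol removal". Section 6.6.5 (non-hematologic toxicity) repeats that sentence. The last row of Table 14, for other non-hematologic toxicity of grade 3 or higher, has a restart instruction that ends at day 21: "If treatment delay is >7 days but ≤21 days, restart treatments following reductions in dosing schedule and drug dosages". It then adds: "If treatment delay >21 days, discontinue study".

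The general part of the DLT definition in Section 4.2.4 also lists "Treatment delays > 21 days".

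**The concern.** A rule for permanently stopping treatment should give one answer for one patient. Here a patient whose toxicity resolves on, say, day 25 of a hold has passed the limit in 6.6.3 or 6.6.5 but not the limit in 6.4. An investigator who works from 6.4 may resume treatment. One who works from 6.6 removes the patient. The trial runs at two institutions (Section 5.7), so the difference could follow the site.

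Two things are at stake. One is patient safety, because the limit decides who is re-exposed after a long toxicity hold. The other is the tolerability result, because the number of patients who discontinue for toxicity depends on which sentence was applied.

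The passages also differ on what ends: study treatment in 6.4, participation in the protocol in 6.6.3 and 6.6.5, and the study itself in Table 14.

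**Working it through.** No statistical figure is involved, so the check is a comparison of the texts.

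**Step 1: do the rules cover the same events?** Section 6.4 speaks of toxicity-related delays and refers treatment-related interruptions to 6.6. Section 6.6 covers events related to study medication. The overlap is therefore direct for toxicities handled in 6.6.3 and 6.6.5. The next sentence of 6.4, on holds unrelated to treatment, is a separate rule and not part of the conflict.

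**Step 2: apply each rule by length of delay, in whole days.**

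| Delay | Section 6.4 | 6.6.3, 6.6.5, Table 14 last row |
|---|---|---|
| 21 days or less | removal not required | removal not required |
| 22 to 28 days | removal not required | removal required |
| 29 days or more | removal required | removal required |

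The band of disagreement is 28 − 22 + 1 = 7 whole-day values. That is 7/21, or one third, of a 21-day cycle.

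**Step 3: look for a tie-break.** Section 6.9.1, which lists reasons to stop treatment, gives no delay limit. It points to drug-specific criteria in Section 7, and Section 7 contains no delay limit either. No other passage ranks 6.4 against 6.6 or confines the 28-day limit to a particular toxicity.

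**Step 4: check the toxicities outside 6.6.3 and 6.6.5.** Section 6.6.4 (tumor lysis) has its own hold instructions and no delay limit. Read section by section, only the 28-day limit reaches those holds. The conflict is therefore shown for hematologic and non-hematologic toxicity, not for every possible hold.

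**Step 5: phase Ib.** The DLT definition uses more than 21 days, and Section 6.5 makes a DLT within the DLT window a reason for protocol removal. That window runs from day 1 to day 21 of cycle 1, so a delay of more than 21 days cannot be completed inside it. If a delay that begins in the window is meant to count, a phase Ib hold of 22 to 28 days would be a DLT leading to removal, although 6.4 would not yet require it. The documents do not settle this, so any reconciled limit needs checking against that item.

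**Step 6: does the wording on what ends change follow-up?** Section 6.9 keeps patients who stop treatment in follow-up. Section 6.9.2 does not list a treatment delay as a reason to leave the study. Section 6.9.4 requires disease assessments to continue after stopping for reasons other than progression, and survival follow-up as well. Section 4.6 requires follow-up data unless consent is withdrawn. Together these indicate that follow-up continues. The Table 14 wording is out of line with them.

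**The case against.** The strongest reply is that 6.4 never says a patient held for 22 to 28 days continues. It only fixes a point beyond which stopping is compulsory, and it defers to 6.6 for interruptions. Removing a patient on day 22 breaks nothing in 6.4, whereas resuming on day 25 breaks the sentence in 6.6.3 or 6.6.5. On this view the shorter limit governs. Section 6.5 also recommends consulting the study PI and medical monitor after significant adverse events, which should reduce divergence between sites.

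Part of this stands. Continuation under 6.4 is an implication, so it would be too strong to say that the protocol orders the same patient to be both kept and removed. The rest does not remove the problem. If the 21-day limit governs, the 28-day sentence has no effect for any toxicity under 6.6.3 or 6.6.5. It would matter only for holds such as those for tumor lysis, and 6.4 is not confined to those. Section 6.5 describes schedule modifications and dosage reductions as suggestions, but the delay limits are written as mandatory. Consultation helps only if those consulted have one rule to apply.

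A reader might also infer that progression-free and overall survival follow-up is lost for patients with the worst toxicity, because Table 14 speaks of ending the study. Sections 4.6, 6.9, 6.9.2 and 6.9.4 point the other way, so this is loose wording and not a demonstrated loss of data.

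**Conclusion.** The inconsistency is real. It is limited to delays of 22 to 28 days for hematologic and non-hematologic toxicity. It rests on the current operative text and needs no assumption beyond taking 6.4 at its word that removal is triggered only above 28 days. Its consequences are possible unequal handling of the same patient at the two sites, with a bearing on patient safety, and a discontinuation count that depends on the passage followed.

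Its frequency cannot be estimated. A reader might turn to Section 4.1, where 2 of 5 patients had grade 4 thrombocytopenia and 2 of 5 had neutropenia of grade 3 or higher. Those are counts of grades, not lengths of holds. They come from the abandoned schedule of 3 days per week, and Section 9.1.1 excludes those patients from the analysis. The only duration reported there is thrombocytopenia of at least 7 days in one patient.

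A reader might also infer a bias in the overall response rate, since one patient among 24 carries 1/24 = 4.2 percentage points. That is the weight of any single patient and does not measure this conflict. The end-of-treatment visit applies whatever the reason for stopping and includes CT, blood immunophenotyping and marrow (Section 1.3), so response can still be documented. No effect on the response rate is shown.

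**What to change.** The sponsor and medical monitor should reconcile Section 6.4, Section 6.6.3, Section 6.6.5 and the last row of Table 14. The text should state the limit or, if more than one is intended, the toxicities to which each applies, including whether tumor lysis holds under 6.6.4 are covered. The result should be checked against the delay item in the DLT definition in Section 4.2.4. The wording on what ends should be made consistent across these places and with Sections 6.9.1, 6.9.2 and 6.9.4, so that it is plain whether follow-up continues. Which limit is right is a clinical decision for the sponsor and medical monitor, and none is proposed here.

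The cost is a wording change in four places plus one cross-check at the next amendment. It adds no patients and no procedures.

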### 6.5 Dose Reductions

In dose-escalation, toxicities that occur within the DLT window that are deemed DLTs (Section 4.1.3 Definition of Dose Limiting Toxicities) will result in protocol removal. Adverse events that are not defined as DLTs, or occur after the DLT window, or occur in patients enrolled in the dose-expansion cohort may lead to dose delays and modifications as detailed in section 6.6. No dose reduction below RP-3500 20mg daily and olaparib 100mg BID will be allowed. Should the protocol dictate a dose reduction of olaparib below 100mg BID and/or RP-3500 below 20mg daily, the patient will be taken off of the protocol therapy. While these are suggested dosing schedule modifications and dosage reductions, the optimal dosing and dosing schedule for each patient should be individualized, and may not always fall into a step-wise fashion. Consultation with the study PI and medical monitor is recommended to determine the optimal dosing for each patient after significant AEs.

## 6.6 Dose Modifications and Supportive Care Guidelines

Subjects experiencing AEs attributed to study drug may undergo dose modifications for toxicity management. Dose modification guidelines are provided below for AEs considered to be related to study medication.

#### 6.6.1 Dosing Schedule Modifications

The dose modifications will first alter the dosing schedules. The dosages of camonsertib (RP-3500) and olaparib will remain the same as the dose to which the patient was originally assigned:

## Table 10.: Dosing Schedule Modifications

Dose Level	Schedule (21 -Day Cycles)	Camonsertib (RP -3500) and Olaparib dosing
Starting	3 weeks on	2 days on/5 days off
-1	2 weeks on/1 week off	2 days on/5 days off during dosing weeks
-2	1 week on/2 weeks off	3 days on/4 days off during dosing weeks

Should the patient require further dose reductions for toxicities, decreases in either camonsertib and/or olaparib dosages can be considered while maintaining the current dosing schedule or concurrently with a dosage decrease and a change in the dosing schedule. The study PI and medical monitor should be contacted for help in determining optimal dosing and dosing schedule for the patient. Some example patient scenarios are presented below:

- Patient experiences grade 3 neutropenic fever for a second time while receiving camonsertib (RP-3500) 50mg daily and olaparib 150mg BID on a dosing schedule of 2 days per week every week (i.e. no off weeks). Dose reduction of camonsertib to 40mg daily and olaparib to 100mg BID can be considered while maintaining the 2 days per week every week (i.e. no off weeks) dosing schedule.
- Patient experiences grade 4 neutropenic fever while receiving camonsertib (RP-3500) 50mg daily and olaparib 150mg BID on a dosing schedule of 2 days per week every week (i.e. no off weeks). Dose reduction of camonsertib to 40mg daily and olaparib to 100mg BID along with reduction of the dosing schedule to 2 weeks on/1 week off may be considered while maintaining the 2 days per week treatment during the dosing/on weeks.

## 6.6.2 Drug Dosage Modifications

After dosing schedule modifications, dosage reductions of either camonsertib and/or olaparib can considered independently or concurrently with dosing schedule modifications. If either camonsertib (RP-3500) or olaparib requires reductions to below DL 1 for toxicity management, study therapy will be discontinued:

Table 11. Dose Reduction Levels

Dose Level	Camonsertib(RP-3500)
1	20mg daily
2	30mg daily

3	40mg daily
4	50mg daily
5	80mg daily

Dose Level	Olaparib
1	100mg BID
2	150mg BID

### 6.6.3 Hematologic and Infectious Toxicities

Optimal supportive care should be offered to the patient in order to mitigate toxicities. Where appropriate, this includes administration of G-CSF, GM-CSF and blood/platelet transfusions as per institutional guidelines. At the start of each cycle, hold therapy until ANC  $\geq$ 500/mm^3 and platelet count is  $\geq$ 25,000/mm^3. Lymphopenia is an expected toxicity of CLL treatments and therefore should be graded and recorded as per CTCAE v5.0, but treatment holds and dose changes are not needed.

This study will utilize the 2018 IWCLL grading scale for hematologic adverse events in patients with baseline platelet count <100,000/mm^3 and/or baseline hemoglobin less than the lower limit of normal. Grading of ANC is at the nadir within the cycle, and patients who have an ANC <1 x  $10^{9}$ /L before therapy will not be evaluable for toxicity. These criteria account for baseline cytopenias secondary to CLL and are detailed in Table 12 below.

Grade	Decrease in platelets or hemoglobin from baseline value, %	Absolute neutrophil count* (nadir) x 10  /L
0	No change to 10	≥2
1	11-24	≥1 and <2
2	25-49	≥1 and <1
3	50-74	≥0.5 and <1
4	≥75	<0.5

Table 12. iwCLL Hematologic Grading

\*If the absolute neutrophil count (ANC) reaches  $<1 \times 10^{9}$ /L, it should be judged to be grade 3 toxicity. Other decreases in the white blood cell count or in circulating granulocytes are not to be considered because a decrease in the white blood cell count is a desired therapeutic end point. A gradual decrease in granulocytes is not a reliable index in CLL for stepwise grading of toxicity. If the ANC was  $<1 \times 10^{9}$ /L before therapy, the patient is not evaluable for toxicity referable to the ANC. The use of G-CSF is irrelevant for the grading of toxicity, but should be documented.

The order in which dose reductions will occur will be change in dosing schedule (Table 10.: Dosing Schedule Modifications) with either sequential (preferred) or concurrent changes in drug dosages (Table 11). If drug dosage changes are required, the order in which dose reductions will occur will be camonsertib (RP-3500) first followed by olaparib if the AE continues to occur. If at any time a dose reduction would leave camonsertib (RP-3500) or olaparib doses less than DL 1 (Table 11. Dose Reduction Levels), the patient will be taken off protocol. Treatment delays for adverse events exceeding 21 days will lead to protocol removal. If reduction of the dosing schedule and/or drug doses resolves the patient's toxicity to grade  $\leq 1$  for at least 3-6 weeks, increasing camonsertib (RP-3500) and/or olaparib back to the prior dose or dosing schedule is permitted after discussion with the study PI.

Event Name	Neutropenia	
Grade of Event	Management/Next Dose for RP - 3500	Management/Next Dose for Olaparib
≤ Grade 1	No change in dose	No change in dose
Grade 2	No change in dose	No change in dose
Grade 3	No change in dose	No change in dose
Grade 4	Hold until ANC ∫ is ≥1000/mm  . G- CSF administration is recommended. At first occurrence, no change in dose or dosing schedule. If toxicity recurs, follow reductions in dosing schedule and drug dosages as per sections 6.6.1 and 6.6.2 only if grade 4 neutropenia lasts ≥7 days with optimal supportive care.	Hold until ANC ∫ is ≥1000/mm  . G- CSF administration is recommended. At first occurrence, no change in dose or dosing schedule. If toxicity recurs, follow reductions in dosing schedule and drug dosages as per sections 6.6.1 and 6.6.2 only if grade 4 neutropenia lasts ≥7 days with optimal supportive care and

Table 13. Management and dose modification guidelines for hematologic toxicities encountered with combination camonsertib (RP-3500) and olaparib.

6.6.2 if RP-3500 dosage already

		RP-3500 dosage already decreased for the same toxicity.	
j Only for patients with ANC $\geq$ 500/mm 	 Only for patients with baseline ANC $\geq$ 1000. For patients with baseline ANC <1000, hold until ANC $\geq$ 500/mm 		
Event Name	Thromboc	ytopenia	
Grade of Event	Management/Next Dose for RP - 3500	Management/Next Dose for Olaparib	
≤ Grade 1	No change in dose	No change in dose	
Grade 2	No change in dose	No change in dose	
Grade 3	Hold until platelets ∫ ≥50,000/mm  . At first occurrence, no change in dose or dosing schedule. If toxicity recurs, follow reductions in dosing schedule and drug dosages as per sections 6.6.1 and 6.6.2.	Hold until platelets J ≥50,000/mm  . At first occurrence, no change in dose or dosing schedule. If toxicity recurs, follow reductions in dosing schedule and olaparib dosages as per sections 6.6.1 and	

		decreased for the same toxicity.
Grade 4	Same management as grade 3	Same management as grade 3
	0 -	

∫Only for patients with baseline platelets ≥100,000/mm^3. For patients with baseline platelets <100,000/mm^3, hold until platelets have recovered to at least 50% of baseline value.

Event Name	Neutropenic Fever	
Grade of Event	Management/Next Dose for RP - 3500	Management/Next Dose for Olaparib
Grade 3	Hold until resolution of toxicity. G- CSF administration required. At first occurrence, no change in dose or dosing schedule. If toxicity recurs, follow reductions in dosing schedule and drug dosages as per sections 6.6.1 and 6.6.2.	Hold until resolution of toxicity. G- CSF administration required. At first occurrence, no change in dose or dosing schedule. If toxicity recurs, follow reductions in dosing schedule and olaparib dosages as per sections 6.6.1 and 6.6.2 if RP-3500 dosage already decreased for the same toxicity.

Grade 4	Hold until resolution of toxicity. G- CSF administration required. Follow reductions in dosing schedule and olaparib dosages as per sections 6.6.1 and 6.6.2.	Hold until resolution of toxicity . G- CSF administration required. Follow reductions in dosing schedule and olaparib dosages as per sections 6.6.1 and 6.6.2.if RP- 3500 dosage already decreased for the same toxicity.
Event Name	Ane	mia
Treat per institutional guidelines including blood transfusions and/or erythropoietins. Consider transfusing for symptoms with hemoglobin >8 g/dL (Grade <3) or for any Grade 3 (hemoglobin		

transfusing for symptoms with hemoglobin >8 g/dL (Grade <3) or for any Grade 3 (hemoglobin <8 g/dL). If possible, maintain RP-3500 and olaparib doses as long as patient is clinically stable, but if a dose reduction or interruption is desired, consult with the Medical Monitor.

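### Section 6.6.3 gives two unreconciled sets of hold levels, the cycle-start rule and the Table 13 recovery levels, that can apply to the same Day 1 count

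*Combined protocol and SAP*

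**What the plan says.** All of this is in Section 6.6.3. Table numbers are those captioned in the body; the front-matter list of tables runs one higher.

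- **Cycle-start rule.** "At the start of each cycle, hold therapy until ANC" is 500/mm³ or more "and platelet count is" 25,000/mm³ or more. It has no qualifier for baseline counts, attribution or a preceding event.
- **Table 13, thrombocytopenia.** For grade 3: "Hold until platelets" are 50,000/mm³ or more. For grade 4: "Same management as grade 3". A footnote restricts the 50,000 level to baseline platelets of 100,000 or more; for lower baselines, "hold until platelets have recovered to at least 50% of baseline value".
- **Table 13, neutropenia.** Grade 4 is held until ANC is 1000/mm³ or more. "For patients with baseline ANC <1000, hold until ANC" is 500/mm³ or more. For grades 1 to 3 the entry is "No change in dose".
- **Consequence of a long hold.** "Treatment delays for adverse events exceeding 21 days will lead to protocol removal". (Section 6.4 gives 28 days for toxicity-related delays; that difference is a separate matter.)

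Section 6.6 limits the dose-modification guidelines to events considered related to study drug. No sentence ranks the cycle-start rule against Table 13 or says that they are cumulative.

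**The concern.** Both rules are phrased as holds that end at a stated count, they sit in the same section, and the counts differ. It is tempting to assign one to cycle starts and the other to events, but the Schedule of Events (Section 1.3) does not keep those occasions apart. From Cycle 3 onward, Day 1 is the only scheduled hematology, so the test that reveals or follows up a grade 3 or 4 event will normally be the cycle-start test. One result can then trigger both rules.

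The choice of reading affects whether a patient is dosed while still thrombocytopenic or neutropenic, how long the delay lasts, and whether it exceeds 21 days and ends protocol participation. The study has two institutions (Section 5.7) and a planned expansion cohort of 24. Different readings could give different exposure and discontinuation for the same counts.

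**Working it through.** The plan has no figure to reproduce. The check sets the two rules side by side and finds the counts at which they differ.

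**Inputs.** The cycle-start and Table 13 levels are those given above. Grade 4 is ANC below 500/mm³, and platelets below 25,000/mm³ when baseline is 100,000 or more (Section 4.2.4). For baseline platelets below 100,000, grade follows the percentage fall: grade 2 is 25 to 49, grade 3 is 50 to 74, grade 4 is 75 or more (Table 12). Baseline platelets below 50,000 and ANC below 1000 are eligible with documented marrow disease (Section 5.1.8).

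**Platelets.** Let B be the baseline. The cycle-start level is 25,000 throughout. The Table 13 level is 50,000 if B ≥ 100,000, otherwise 0.5 × B. The two are equal when 0.5 × B = 25,000, that is, B = 50,000.

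| Baseline B | Table 13 level | Day 1 counts where the rules differ | Direction |
|---|---|---|---|
| 100,000 or more, after a fall below 25,000 | 50,000 | 25,000 to 49,999 | cycle-start level met, Table 13 still holds |
| 80,000 | 40,000 | 25,000 to 39,999 | same |
| 60,000 | 30,000 | 25,000 to 29,999 | same |
| 50,000 | 25,000 | none | levels coincide |
| 40,000 | 20,000 | 20,000 to 24,999 | reversed: Table 13 level met, cycle-start rule holds |

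Worked cases:

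- B ≥ 100,000, nadir below 25,000 (grade 4), Day 1 count 30,000. Since 30,000 ≥ 25,000, the cycle-start level is met; since 30,000 < 50,000, Table 13 holds.
- B = 60,000, Day 1 count 28,000. The fall is (60,000 − 28,000) / 60,000 = 53%, grade 3 in Table 12. Table 13 holds until 0.5 × 60,000 = 30,000; the cycle-start level is met.
- B = 40,000, Day 1 count 22,000. The fall is (40,000 − 22,000) / 40,000 = 45%, grade 2, for which Table 13 asks for no dose change, and the count is above 0.5 × 40,000 = 20,000. The cycle-start rule holds because 22,000 < 25,000.

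**ANC.** With baseline 1000 or more, after grade 4 neutropenia, the levels are 500 (cycle start) and 1000 (Table 13), so they differ for Day 1 counts of 500 to 999. If the nadir was grade 3, Table 13 imposes no hold and there is no mismatch. With baseline below 1000 both levels are 500 and there is none.

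**Does reading the first rule as a general minimum resolve it?** For treatment-related events, ANC below 500 is already grade 4 and held by Table 13. Platelets below 25,000 are grade 4 when B ≥ 100,000, and a fall of more than 50% (grade 3 or higher) when B is 50,000 to 99,999, so Table 13 already holds them too. On that reading the cycle-start sentence adds a restriction for treatment-related events only when baseline platelets are below 50,000. A site could therefore reasonably take it as a separate Day 1 restart rule.

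**The case against.** The strongest reply is that the rules are not logically incompatible. Each says when to hold; neither orders dosing once its level is reached. They can be applied together as a general minimum plus event-specific recovery levels, and their scopes differ, because the cycle-start sentence names no attribution and so can also cover cytopenia due to CLL. Section 6.5 calls the modifications suggestions to be individualized, and Sections 6.5 and 6.6.1 send difficult cases to the study PI and medical monitor.

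This stands in part. A reader might infer that the plan instructs dosing at platelets of 25,000; it does not. But it also does not state the cumulative reading, and consultation does not say which level governs. The rule for conflicting recommendations in Section 6.6.5 is placed under non-hematologic toxicities and concerns several simultaneous events, so it does not settle the matter.

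Other stronger readings also fail:

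- *The holds distort the compliance-based analysis set.* Section 9.2.2.2 exempts doses missed to manage treatment-related toxicity, and Table 13 holds are of that kind.
- *The first five patients show that these counts will occur.* The 2/5 with grade 4 thrombocytopenia and 2/5 with grade 3 or higher neutropenia (Section 4.1) were on the abandoned 3-day weekly schedule. The platelet grades are iwCLL percentage falls without baselines or Day 1 counts, and the number with grade 4 neutropenia is not given. The figures cannot be mapped to the bands above.
- *Any platelet count of 25,000 to 49,999 with a baseline of 100,000 or more is affected.* Without a preceding grade 4 event this depends on CTCAE cut-offs that the documents do not print.
- *Sites will differ.* That is possible, but the documents do not show it.

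**Conclusion.** The concern holds as an unreconciled pair of safety rules. It is clearest for platelets, where Table 13 is the stricter rule for baselines above 50,000, the cycle-start rule is the stricter one below 50,000, and they agree only at 50,000. For ANC it is confined to counts of 500 to 999 after grade 4 neutropenia with baseline ANC of 1000 or more.

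The conclusion assumes that the event is treatment-related, so that Table 13 applies, and for baseline platelets of 100,000 or more that the count had fallen below 25,000. How often such counts will arise on the 2-day schedule cannot be estimated from the documents. What can be said is that identical Day 1 results permit different actions, with consequences for dosing during cytopenia, length of delay and removal. This should be corrected; it does not undermine the design or the primary analysis.

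**What to change.** The clinical team should reconcile the cycle-start sentence with Table 13 and its footnotes, and state in Section 6.6.3 how the two combine on Day 1 of a cycle. The statement should cover a patient still under a Table 13 hold, patients with baseline platelets below 100,000 and in particular below 50,000, and recovery from grade 4 neutropenia. It should also say whether the cycle-start rule applies to cytopenia not attributed to study drug. Which levels are clinically right is for the clinical team; none is proposed here.

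The cost is a sentence or two in the next amendment, with no change to sample size, endpoints or analysis.
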